Specific Aim 2: Conduct a feasibility pilot of our dietary behavioral intervention through a hybrid I implementation randomized controlled design in 80 NMIBC survivors, where the treatment group (n=40) will receive an evidence-based telephone intervention to increase cruciferous vegetable intake and the control group (n=40) will receive a general fruit and vegetable intake intervention based on NCI guidelines. The primary outcomes will be cruciferous vegetable intake and urinary ITC levels, and the secondary outcome will be gene expression changes in urinary exfoliated epithelial cells as a surrogate for intermediate efficacy.

Exploratory Aim: Engage the clinical care providers of patients enrolled in our intervention to ascertain the barriers and facilitators of intervention implementation within clinical practice through conducting 20 semi-structured interviews. The goal is to gain feedback and refine the intervention for “real-world” implementation.

Primary Objective(s)

- Develop an evidence-based behavioral intervention to increase cruciferous vegetable intake, with the goal of attaining desirable urinary ITC levels effective for anti-cancer activities. We will work with our Community Advisory Board to adapt materials and methods from current evidence-based fruit and vegetable interventions and leverage

our findings on ITC yield from cruciferous vegetables to develop our dietary intervention, using a systematic process consisting of information gathering, discussion groups, and mock intervention delivery.

- Conduct a feasibility pilot of our dietary behavioral intervention through a hybrid I implementation randomized controlled design in 80 NMIBC survivors, where the treatment group (n=40) will receive an evidence-based telephone intervention to increase cruciferous vegetable intake and the control group (n=40) will receive a general fruit and vegetable intake intervention based on NCI guidelines. The primary outcomes will be cruciferous vegetable intake and urinary ITC levels.

Secondary Objective(s)

- The secondary outcome will be to ascertain the level of gene expression changes in urinary exfoliated epithelial cells (due to the intervention) as a surrogate for intermediate efficacy.

Exploratory Objective(s)

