8. STUDY ENDPOINTS

Primary Endpoint(s)

- Urinary ITC levels will be measured using HPLC-based cyclocondensation assay^{14, 51}, which measures ITCs and metabolites as low as a few picomoles and has been routinely performed in [name] laboratory. The results will be adjusted by urinary creatinine level using creatinine assay kits (Caymen, Ann Arbor, MI). Cruciferae intake will be assessed using a questionnaire adapted from Thomson et al.⁵² to capture both intake and cooking styles.

Secondary Endpoint(s)

- Gene expression will be evaluated via RNA-seq as a surrogate for intermediate efficacy, conducted at Roswell Park's Genomics Shared Resource using NextSeq500 platform (Illumina Inc.). We have worked with the Genomics core to optimize the extraction of RNA samples from urine. With the addition of TRIzol™ right before the storage of the cell pellet samples, we were able to extract sufficient amounts of RNA and generate high quality RNA-seq data. Dietary intake will be evaluated by three non-consecutive 24-hour dietary recalls (two weekdays, one weekday) conducted by trained staff using the interview-administered Nutrition Data System for Research (NDSR)⁵³.
- Additional urinary metabolites and potential biomarkers will be explored using proteomic and/or metabolomic approaches.

Exploratory Endpoint(s)

- Our exploratory endpoint will be identification of barriers, facilitators, and other process-related measures relevant to informing the implementation of an evidence-based cruciferae intervention within clinical practice.

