30. **During the past month, how many times per week did you eat dark green vegetables for example broccoli or dark leafy greens including romaine, chard, collard greens or spinach?**

 times per week

31. **During the past month, how many times per week did you eat orange-colored vegetables such as sweet potatoes, pumpkin, winter squash, or carrots? (write number)**

32. **Not counting the vegetables mentioned, about how many times per week did you eat OTHER vegetables? Examples of other vegetables include tomatoes, tomato juice or V-8 juice, corn, eggplant, peas, lettuce, cabbage, and white potatoes that are not fried such as baked or mashed potatoes. (write number)**

 times per week

These next questions are about other vegetables you ate during the **past 30 days**. Please think about all meals, snacks, and food consumed at home and away from home.

(Go through table. Frame questions as, “How often did you eat raw arugula? Never, a few times per year, once per month, 2-3 times per month, once a week, twice per week, 3-4 times per week, 5-6 times per week, or every day.” If they answer never, go to the next vegetable. If they ate any amount, ask, “About how much raw arugula did you eat each time? The medium serving size is one cup of the vegetable, about the size of a baseball. Lightly cooked generally includes stir fry, sauté, microwave, short-term, e.g. less than 10 minutes, steam or bake, and thoroughly cooked includes stew, biol, or long-term, e.g. more than 10 minutes, steam or bake.)

Vegetables

		Never	A Few Times Per Year	Once per month	2-3 Times per month	Once per week	Twice per week	3-4 Times per week	5-6 Times per week	Every day	How much each time?		
											S	M	L
Arugula	raw												
	lightly cooked (e.g. stir fry)												
	thoroughly cooked (e.g. stew)												
Broccoli	raw												
	lightly cooked (e.g. stir fry)												
	thoroughly cooked (e.g. stew)												
Broccoli sprout	raw												
	lightly cooked (e.g. stir fry)												
	thoroughly cooked (e.g. stew)												
Broccolini	raw												
	lightly cooked (e.g. stir fry)												
	thoroughly cooked (e.g. stew)												

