	lightly cooked (e.g. stir fry)										
	thoroughly cooked (e.g. stew)										
Chinese cabbage/ Napa	raw										
	lightly cooked (e.g. stir fry)										
	thoroughly cooked (e.g. stew)										
Daikon root	raw										
	lightly cooked (e.g. stir fry)										
	thoroughly cooked (e.g. stew)										
Celery	raw										
	lightly cooked (e.g. stir fry)										
	thoroughly cooked (e.g. stew)										
Garden cress	raw										
	lightly cooked (e.g. stir fry)										
	thoroughly cooked (e.g. stew)										
Water cress	raw										

	lightly cooked (e.g. stir fry)										
	thoroughly cooked (e.g. stew)										
Radicchio	lightly cooked (e.g. stir fry)										
	thoroughly cooked (e.g. stew)										
Radishes	raw										
	lightly cooked (e.g. stir fry)										
	thoroughly cooked (e.g. stew)										

We're going to finish the survey by asking some final questions about sauces and condiments you ate during the **past 30 days**. Please think about all meals, snacks, and food consumed at home and away from home.

(Go through table. Frame questions as, "How often did you eat mayonnaise? Never, a few times per year, once per month, 2-3 times per month, once a week, twice per week, 3-4 times per week, 5-6 times per week, or every day." If they answer never, go to the next food. If they ate any amount, ask, "About how much mayonnaise did you eat each time? The size of your thumb from knuckle to tip or less? About two thumbs worth? Or more than 2 thumbs worth?"

For **horseradish**, if they consume any amount, ask, "about how much horseradish did you eat each time? Smaller than an egg, about the size of egg, or more than the size of an egg?")

SAUCES AND CONDIMENTS											
	Never	A Few Times Per Year	Once per month	2-3 Times per month	Once per week	Twice per week	3-4 Times per week	5-6 Times per week	Everyday	Medium Serving	Serving Size
											S
											M L

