25. During the past month, how many times per week did you drink 100% PURE fruit juices? Do not include fruit-flavored drinks with added sugar or fruit juice you made at home and added sugar to. Only include 100% juice.

____ times per week

26. During the past month, not counting juice, how many times per week did you eat fruit? Count fresh, frozen, or canned fruit.

____ times per week

27. During the past month, how many times per week did you eat cooked or canned beans, such as refried, baked, black, garbanzo beans, beans in soup, soybeans, edamame, tofu or lentils. Do NOT include long green beans.

____ times per week

28. During the past month, how many times per week did you eat dark green vegetables for example broccoli or dark leafy greens including romaine, chard, collard greens or spinach?

____ times per week

29. During the past month, how many times per week did you eat orange-colored vegetables such as sweet potatoes, pumpkin, winter squash, or carrots? (write number)

30. Not counting the vegetables mentioned, about how many times per week did you eat OTHER vegetables? Examples of other vegetables include tomatoes, tomato juice or V-8 juice, corn, eggplant, peas, lettuce, cabbage, and white potatoes that are not fried such as baked or mashed potatoes. (write number)

____ times per week

These next questions are about other vegetables you ate during the **past 30 days**. Please think about all meals, snacks, and food consumed at home and away from home.

(Go through table. Frame questions as, “How often did you eat raw arugula? Never, a few times per year, once per month, 2-3 times per month, once a week, twice per week, 3-4 times per week, 5-6 times per week, or every day.” If they answer never, go to the next vegetable. If they ate any amount, ask, “About how much raw arugula did you eat each time? The medium serving size is one cup of the vegetable, about the size of a baseball. Lightly cooked generally includes stir fry, sauté, microwave, short-term, e.g. less than 10 minutes, steam or bake, and thoroughly cooked includes stew, biol, or long-term, e.g. more than 10 minutes, steam or bake.)

Vegetables		Never	A Few Times Per Year	Once per month	2-3 Times per month	Once per week	Twice per week	3-4 Times per week	5-6 Times per week	Every day	How much each time?	S	M	L
Arugula	raw													
	lightly cooked (e.g. stir fry)													

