- Alternatively you can dry them out in your oven at the lowest possible temperature, place the leaves in the oven on a baking sheet for about 5 to 10 minutes.
- Either way you want the mint to be dry but still green.

Source: yeprecipes.com

[figure not shown]

14 POW-R HEALTH: Power to Redefine Your Health

Which power vegetables are high in ITCs?

POW-R HEALTH: Power to Redefine Your Health 17

How about frozen power vegetables?

It is okay to freeze and eat power vegetables that have been frozen, but fresh is best. Just as you may have eaten fresh (not canned) vegetables when you were growing up, it is best to eat power vegetables fresh. Fresh is best because the amount of isothiocyanates may decrease from the freezing process. Fresh vegetables also have more nutrients that are good for your health. So, eating frozen power vegetables are okay, but fresh is always best.

8 POW-R HEALTH: Power to Redefine Your Health

What is the best way to eat power vegetables?

It is best to eat power vegetables fresh, or raw. Just like the good old days, when most vegetables were eaten fresh, it is best to eat power vegetables fresh. They can be lightly cooked too. How you cook and how long you cook will affect how much isothiocyanates a power vegetable will give you. Cooking power vegetables too much can reduce isothiocyanates. Don't use canned power vegetables. Just like in the old days when vegetables were homegrown and not canned, stay away from canned power vegetables.

DO eat power vegetables fresh or raw, or cooked a little bit (less than 10 minutes), such as:

- stir frying
- sautéing
- microwaving
- steaming

DON'T overcook (more than 10 minutes):

- stewing
- boiling
- baking

My personal action plan to eat more power vegetables

Today's Date: _____

My reasons for wanting to eat more power vegetables

The most important reasons I _____ want to eat more power vegetables are:

My power vegetable eating goals

In 6 months, I pledge to eat _____ serving(s) of power vegetables each day. My short-term goal is to eat _____ serving(s) this week, between (dates) _____ and _____.

Who can help me

This person can help me eat more power vegetables:

Obstacles and strategies

The obstacles that may make it harder for me to reach my goals and the strategies I can use to overcome them are:

Obstacles	Strategies
Obstacle 1	Strategy 1
	Strategy 2
	Strategy 3
Obstacle 2	Strategy 1
	Strategy 2
	Strategy 3

My plan this week to eat more power vegetables

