- **Fresh** fruit is best! Fresh fruit usually gives your body the most nutrients. Try to eat as many different types of fruit as you can.
- **Frozen** fruit can last longer than fresh fruit and can be cheaper to buy.
- **Canned** fruit can be high in sugar and calories, so buy canned fruit in 100% fruit juice with no sugar added.

How many fruits and vegetables are you supposed to eat?

- Eat **2 1/2 to 3 cups of vegetables** and **1 1/2 to 2 cups of fruit** each day. 1/2 cup is about the size of the front part of your fist. 1 cup is about the size of a baseball.

SERVING SIZES

POW-R HEALTH: Power to Redefine Your Health

5

12 POW-R HEALTH: Power to Redefine Your Health

How to prepare fruits and vegetables

You can eat a lot of fruits and vegetables raw. You can also cook them in many different ways:

- sautéeing
- microwaving
- steaming
- baking
- stir-frying
- stewing
- boiling

Tips on how to eat more fruits and vegetables

You can buy fruits and vegetables from many different places. You can buy them from your local grocery store, farmer's market, and online. Here are some tips on how to eat more fruits and vegetables:

- Have a healthy morning. Add sliced fruit, like a sliced banana, to your cereal for breakfast.

Source: simplyrecipes.com

Cucumber Salad with Grapes and Almonds

Cucumber salad with grapes, toasted almonds and a little garlic—essentially a deconstructed white gazpacho! Perfectly balanced, cool and refreshing summer salad.

Servings: 4 people

Prep Time: 30 minutes

Cook Time: 5 minutes

INGREDIENTS

- 1/4 cup slivered and blanched almonds
- 1 pound cucumbers, peeled if the peel is bitter, unpeeled if not
- Kosher salt
- 1 teaspoon minced garlic
- About 20 green grapes, sliced in half
- 2 tablespoons extra-virgin olive oil
- 1 teaspoon sherry or white wine vinegar
- 2 teaspoons minced chives, for garnish

INSTRUCTIONS

1. Prep the cucumbers: Slice the cucumbers in half lengthwise. Use a spoon to scoop out the seeds in the middle, discard the seeds. If using rather large cucumbers, slice them again lengthwise. Then cut them crosswise into 1/4-inch to 1/2-inch slices.
- Place in a large bowl and sprinkle with a teaspoon of kosher salt. Toss to distribute the salt evenly around the cucumber pieces.
- Let sit for 20 to 25 minutes while the salt helps pull excess moisture out of the cucumbers.

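### As printed, the intake interview skips a vegetable's cooked rows after a 'never' to raw, so cruciferae intake may be under-recorded at both visits, with unknown effect on the arm difference

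*Combined protocol and SAP*

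**What the plan says.** Section 1 states: "The primary outcomes will be cruciferous vegetable intake and urinary ITC levels". Section 8 assigns the intake outcome to one instrument, an adapted questionnaire intended "to capture both intake and cooking styles". The 24-hour dietary recalls appear in the same section under secondary endpoints.

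The questionnaire is printed in Appendix F (baseline) and Appendix G1 (6 months). In its vegetable table each vegetable has separate rows for raw, lightly cooked and thoroughly cooked, except a few that have only the two cooked rows. The model question concerns one preparation: "How often did you eat raw arugula". The instruction that follows is "If they answer never, go to the next vegetable. If they ate any amount, ask" the amount eaten each time. Appendix G1 repeats it: "If they answer never, go to the next vegetable".

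The two arms receive different advice on preparation (Appendix P). The intervention magazine says "It is best to eat power vegetables fresh, or raw" and also accepts light cooking. The control magazine says of fruits and vegetables that many can be eaten raw, then "You can also cook them in many different ways", and its list includes stewing and boiling.

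Section 11 says that answers go directly into pre-programmed REDCap forms. Their branching is not shown.

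**The concern.** The question is asked per preparation, but the skip is by vegetable. A participant who says *never* to raw broccoli is taken to broccoli sprouts, and stir-fried or steamed broccoli is not asked about. Nothing in either form returns to the skipped rows.

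At stake is the measurement of a primary outcome at both visits. Whether a cooked row is reached depends on raw use, and the arms are advised differently about raw use. The intake lost at 6 months may therefore differ between arms for reasons unrelated to how much people eat.

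**Working it through.** **1. Rows at risk (Appendix F; Appendix G1 is the same).** The table has 26 vegetables. Leaving out corn, carrots, peas, celery and radicchio gives 21 cruciferae (sauerkraut counted as cabbage). Eighteen have three rows starting with raw. Three (collard greens, turnip, turnip greens) have two rows starting with lightly cooked.

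- Rows: 18 × 3 + 3 × 2 = 60.
- Always asked: the first row of each vegetable, 21.
- Asked only after earlier answers: 60 − 21 = 39, of which 18 × 2 = 36 lie behind a raw row and 3 behind a lightly cooked row.

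**2. The skip beside its neighbours.**

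| Place | Question level | Where a negative answer leads |
|---|---|---|
| Appendices F and G1, vegetables | vegetable × preparation | next vegetable |
| Appendices F and G1, condiments | food, one row each | "If they answer never, go to the next food", which is the next row |
| Appendix D, urine questionnaire | vegetable first, preparation only if eaten | next vegetable |

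The condiment rule loses nothing because each food has one row. Appendix D loses nothing because preparation is asked after the vegetable. Only the vegetable table puts a vegetable-level skip behind a preparation-level question.

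**3. Two single-person examples under the literal rule.** Assume 75 g per portion, the typical serving in Section 19.

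- *Recorded rise too large.* Lightly cooked broccoli 3–4 times a week, never raw: true baseline 3.5/7 × 75 = 37.5 g/day, recorded 0. The person then adds raw broccoli once a month: 75/30.4 = 2.5 g/day. The raw row is now positive, the cooked row is reached, and 37.5 + 2.5 = 40.0 g/day is recorded. True rise 2.5, recorded rise 40.0.
- *Recorded rise too small.* No broccoli at baseline, then stir-fried broccoli 3–4 times a week, never raw: true rise 37.5 g/day, recorded rise 0.

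Both people have followed the intervention's advice. They show that the error can go either way; they do not estimate a group effect.

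**4. The plan's own power figure (Section 19), for scale.** Inputs: 40 per arm, 0.57 SD, R² = 0.2, two-sided 0.05, SD 62 g/day.

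- 0.57 × 62 = 35.3 g/day.
- SE = 62 × √(1 − 0.2) × √(2/40) = 12.4 g/day.
- Noncentral t with 80 − 3 = 77 df and noncentrality 35.3/12.4: power 80%. The plan's 80% is reproduced and does not depend on the skip.

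**5. Group-level scenarios.** The documents do not say what share of intake comes from preparations that the skip would hide, so the shares are assumptions. The loss is applied to 6-month intake. Baseline loss is equal between arms in expectation because of randomization. SD (62) and R² (0.2) are held fixed.

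No true difference, both arms at 52.7 g/day; false difference = 52.7 × gap in loss:

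| Gap in share lost between arms | False difference, g/day | Chance of p < 0.05 |
|---|---|---|
| 0 | 0 | 5% |
| 10 points | 5.3 | 7% |
| 20 points | 10.5 | 13% |
| 30 points | 15.8 | 24% |
| 40 points | 21.1 | 39% |

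The sign follows whichever arm loses more: a larger loss in control favours the intervention, and a larger loss in the intervention arm favours control.

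True difference 35.3 g/day (52.7 + 35.3 = 88.0 v 52.7); recorded difference = 88.0 × (1 − loss, intervention) − 52.7 × (1 − loss, control):

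| Loss, intervention | Loss, control | Recorded difference, g/day | Power |
|---|---|---|---|
| 0% | 0% | 35.3 | 80% |
| 20% | 20% | 70.4 − 42.2 = 28.2 | 61% |
| 10% | 30% | 79.2 − 36.9 = 42.3 | 92% |
| 30% | 10% | 61.6 − 47.4 = 14.2 | 20% |

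The 61% depends on the fixed SD. If every person lost exactly 20%, the SD would shrink too and power would not change. Under the skip, loss is all-or-nothing by person and vegetable, so uniform shrinkage is unlikely, but the resulting SD cannot be derived.

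**The case against.** The strongest objection is that the interview may not run this way. The interviewer is told to go through the table and is given a template, its example item is raw arugula, and the portion question also refers to raw arugula. *Next vegetable* could therefore mean the next line, as the matching phrase does for condiments. The literal reading would defeat the instrument's purpose of recording cooking style, and the REDCap form may already present every row. This stands as far as it goes: the loss is conditional on practice that the documents do not show. It does not remove the point. The left-hand column names vegetables, neither form mentions a next row or preparation, and the staff training described in Section 11 concerns intervention delivery, not this interview.

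A reader might go further and infer that the skip biases the trial towards the intervention, because only that arm is taught that raw is best and new raw use would reveal existing cooked intake. The documents do not support that. Section 2 says light cooking increases ITC yield and plans to recommend it. The intervention magazine endorses stir-frying, sautéing, microwaving and steaming, its action plan offers five preparations of which four are cooked, and its recipes include cooked greens. Light cooking taken up without raw use would be missed, which shrinks the difference.

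It can also be said that other measures cover the gap. Urinary ITC, the other primary outcome, is untouched, and the recalls do not use this skip. But the recalls are secondary and cover three days per assessment, against a 30-day questionnaire for the primary outcome.

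**Conclusion.** The point holds in conditional form. It is certain that the printed rule, followed literally, leaves up to 39 of the 60 cruciferae rows unasked, at both visits. It is not known whether interviewers or REDCap follow it. If they do, a primary outcome is under-recorded, and the loss at 6 months may differ by arm. Neither direction nor size follows from the documents. The scenario figures are illustrations that rest on assumed loss shares and a fixed SD and R²; they are not estimates of bias in this trial. No sample size or power figure in the plan is wrong on this account. The correction is worth making because it costs little and the outcome affected is primary.

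**What to change.** **Forms.** In Appendices F and G1, reword the instruction along these lines: *after a never, go to the next preparation row of the same vegetable; move to the next vegetable only when all its rows have been asked.* A *never* should skip only that row's portion question. Confirm that the REDCap branching does the same.

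**Data already collected.** Check whether cooked rows are blank whenever raw was answered *never*. If they are not, the rewording is enough. If they are:

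- do not score the blanks as zero without comment. Setting them all to missing is not workable either: few people are likely to eat all 18 raw-first vegetables raw (garden cress, kohlrabi and daikon are among them), so nearly every total would be incomplete;
- ask all rows at every remaining 6-month interview;
- record which form version each participant had at each visit. Section 11 provides for participants who had already finished follow-up by the March 2022 revision, so some may have had the printed rule at both visits and others at baseline only;
- do not report within-person change for participants whose two visits used different versions, because the change of form would be mixed with the change in diet. This affects the planned paired t-tests and pre–post summaries directly;
- report cruciferae intake from the 24-hour recalls as a sensitivity analysis for the arm comparison.

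**Cost.** One line in two forms, a branching check, a slightly longer call for some participants and one added sensitivity analysis.
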